#### 7.1.6. Summaries of Adverse Events and Death

The number and percentage of subjects who experienced at least 1 TEAE will be provided and summarized by SOC, HLT, PT, and treatment group. For other AEs described below, summaries will be provided by SOC, PT, and treatment group. All AEs summary will use both the Safety Analysis Set for randomized phase analysis and All B/F/TAF Analysis Set for all B/F/TAF analysis, respectively.

- Any Grade 2, 3, or 4 treatment-emergent AEs
- Any Grade 3 or 4 treatment-emergent AEs
- All treatment-emergent study drug-related AEs

- Any Grade 2, 3, or 4 treatment-emergent study drug-related AEs
- Any Grade 3 or 4 treatment-emergent study drug-related AEs
- All treatment-emergent SAEs
- All treatment-emergent study drug-related SAEs
- All treatment-emergent AEs that caused premature discontinuation from study drug

A brief, high-level summary of AEs described above will be provided by treatment group and by the number and percentage of subjects who experienced the above AEs. Treatment-emergent deaths observed in the study will be also included in this summary.

Treatment-emergent death refers to deaths that occurred between the first dose date and the last dose date plus 30 days (inclusive).

Multiple events will be counted only once per subject in each summary. Adverse events will be summarized and listed first in alphabetic order of SOC and HLT within each SOC (if applicable), and then by PT in descending order of total frequency within each SOC. For summaries by severity grade, the most severe grade will be used for those AEs that occurred more than once in an individual subject during the study.

In addition to the above summary tables, all treatment-emergent AEs, Grade 3 or 4 treatment-emergent AEs, treatment-emergent study drug-related AEs, Grade 2, 3, or 4 treatment-emergent study drug-related AEs, and treatment-emergent SAEs will be summarized by PT only, in descending order of total frequency.

Summary of treatment-emergent AEs by SOC and PT will also be conducted for all subgroups listed in Section 3.4.2 for randomized phase analysis.

In addition, data listings will be provided for the following:

- All AEs
- Grade 3 and 4 AEs
- SAEs
- Study-Drug-Related SAEs
- Deaths report
- AEs leading to premature discontinuation of study drug

# 7.1.7. Additional Analysis of Adverse Events

## 7.1.7.1. Stage 3 Opportunistic Illnesses in HIV

On an ongoing basis, AEs will be reviewed for events that might meet the definition of stage 3 opportunistic illnesses in HIV that are indicative of an AIDS-defining diagnoses (see Appendix 6 of the protocol). The Gilead medical monitor will review the possible stage 3 opportunistic illnesses and approve the events that meet the definition. Events that meet the stage 3 opportunistic illness definition of an AIDS-Defining Diagnosis will be listed.

#### 7.1.7.2. Cardiovascular or Cerebrovascular Events

Preferred terms for cardiovascular or cerebrovascular events are from relevant Standardized MedDRA Query (SMQ). The selected PT listing was provided by GLPS and reviewed by Gilead medical monitors (see details in Appendix 5).

The number and percentage of subjects with treatment-emergent cardiovascular or cerebrovascular events and serious cardiovascular or cerebrovascular events by PT will be summarized by treatment group based on the safety analysis set for randomized phase analysis and All B/F/TAF Analysis Set for all B/F/TAF analysis, respectively. Statistical comparisons of the subject incidence rates between the 2 treatment groups will be performed using the Fisher's exact test for randomized phase analysis. No statistical comparisons of the subject incidence rates between the 2 treatment groups will be performed for all B/F/TAF analysis. A data listing of cardiovascular or cerebrovascular events will be provided.

## 7.1.7.3. Hepatic Events

Preferred terms for hepatic events are from 15 relevant SMQs, which are identified as non-infectious and non-congenital hepatobiliary disorders. The selected PT listing was provided by Gilead GLPS and reviewed by Gilead medical monitors (see details in Appendix 6).

The number and percentage of subjects with treatment-emergent hepatic events and serious hepatic events by PT will be summarized by treatment group based on the safety analysis set for randomized phase analysis and All B/F/TAF Analysis Set for all B/F/TAF analysis, respectively. Statistical comparisons of the subject incidence rates between the 2 treatment groups will be performed using the Fisher's exact test for randomized phase analysis. No statistical comparisons of the subject incidence rates between the 2 treatment groups will be performed for all B/F/TAF analysis. A data listing of hepatic events will be provided.

#### 7.1.7.4. COVID-19

A data listing of TEAEs for COVID-19 and Suspected COVID-19 infection (see definition in Appendix 4) will be provided.

# 7.2. Laboratory Evaluations

Laboratory data collected during the study will be analyzed and summarized using both quantitative and qualitative methods. Summaries of laboratory data will be provided based on the Safety Analysis Set for randomized phase analysis and All B/F/TAF Analysis Set for all B/F/TAF analysis, respectively. The analysis will be based on values reported in conventional units. When values are below the LOQ, they will be listed as such, and the imputed value will be used for the purpose of calculating summary statistics as specified in Section 3.7.

A by-subject listing for laboratory test results will be provided by subject ID number and visit in chronological order for hematology, serum chemistry, and urinalysis separately. Values falling outside of the reference range and/or having a severity grade of 1 or higher on the Gilead Grading Scale for Severity of Adverse Events and Laboratory Abnormalities will be flagged in the data listings, as appropriate.

No formal statistical testing is planned.

#### 7.2.1. Summaries of Numeric Laboratory Results

Descriptive statistics will be provided by treatment group based on the safety analysis set for randomized phase analysis and All B/F/TAF Analysis Set for all B/F/TAF analysis for each laboratory test specified in the study protocol as follows:

- Baseline values
- Values at each postbaseline analysis window
- Change from baseline at each postbaseline analysis window
- Percentage change from baseline to each postbaseline analysis window (if specified)

A baseline laboratory value will be defined as the last nonmissing value obtained on or prior to the date of first dose of study drug. Change from baseline to a postbaseline visit will be defined as the postbaseline value minus the baseline value. The mean, median, Q1, Q3, minimum, and maximum values will be displayed to the reported number of digits; SD values will be displayed to the reported number of digits plus 1.

In the case of multiple values in an analysis window, data will be selected for analysis as described in Section 3.8.3.

#### **Calcium Corrected for Albumin**

Calcium corrected for albumin will be calculated and summarized for the study. The following formula will be used when both serum calcium and albumin results for a given blood drawn are available and serum albumin value is < 4.0 g/dL.

• Calcium corrected for albumin (mg/dL) = serum calcium (mg/dL) +  $0.8 \times (4.0 - \text{albumin (g/dL)})$ .

Toxicity grading for calcium will be applied based on the corrected values.

#### **Estimated GFR**

The following formula will be used to calculate eGFRCG:

• eGFR(CG) (mL/min) =  $[(140 - age (years)) \times weight (kg) \times (0.85 \text{ if female})] / (SCr (mg/dL) \times 72)$ , where weight is total body mass in kilograms, and SCr is serum creatinine.

## 7.2.2. Graded Laboratory Values

The Gilead Grading Scale for Severity of Adverse Events and Laboratory Abnormalities will be used for assigning toxicity grades (0 to 4) to laboratory results for analysis. Grade 0 includes all values that do not meet the criteria for an abnormality of at least Grade 1. For laboratory tests with criteria for both increased and decreased levels, analyses for each direction (ie, increased, decreased) will be presented separately.

If there is any laboratory toxicity grading scale overlapping with the normal reference ranges (eg, grade 1 scale overlaps with normal reference ranges), laboratory values that are within the normal range will be grade 0 except for lipid tests.

For triglycerides, LDL, and cholesterol, the protocol specified toxicity grading scale is for fasting test values, so non-fasting lipid results (or lipid results without known fasting status) will not be graded or summarized by toxicity grades.

#### 7.2.2.1. Treatment-Emergent Laboratory Abnormalities

Treatment-emergent laboratory abnormalities are defined as values that increase at least 1 toxicity grade from baseline at any postbaseline time point, up to 30 days after permanent discontinuation of study drug. If the relevant baseline laboratory value is missing, any abnormality of at least Grade 1 observed within the time frame specified above will be considered treatment emergent.

Fasting glucose and nonfasting glucose (including glucose results without a known fasting status) are graded based on different grading scales as specified in the protocol. Treatment-emergent laboratory abnormalities will be summarized for fasting glucose. Maximum postbaseline grade, instead of treatment-emergent grade, for nonfasting glucose (including glucose results without a known fasting status) will be summarized, as nonfasting glucose was not assessed at baseline visit for most of the subjects; therefore, an abnormality is treatment-emergent or not cannot be determined for these subjects.

Both urine red blood cell (RBC) based on microscopic examination, labeled as Hematuria (Quantitative), and urine blood based on a dipstick, labeled as Hematuria (Dipstick), are assessed and assigned a toxicity grade in this study. Hematuria (Quantitative) is a reflex test. Urine RBC based on microscopic examination or dipstick will be presented in laboratory toxicity summary tables and listings.

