For all eligible subjects, blood and urine will be collected at Day 1, Weeks 4, 8, 12, and then every 12 weeks through the End of Blinded Treatment Visit. Laboratory analyses (hematology, chemistry, and urinalysis), HIV-1 RNA, CD4+ cell count and percentage, and complete or symptom-directed physical examinations will be performed at the Screening, Day 1, and all subsequent study visits.

Adverse events and concomitant medications will be assessed at each visit.

Historical HIV-1 RNA genotypes (from resistance testing) will be collected, if available.

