## 6.10.1. Blood Samples

- Blood sample collection for the following laboratory analyses:
  - Serum pregnancy test (females of childbearing potential only). If the test is positive, the subject will not be enrolled
  - Chemistry profile: alkaline phosphatase, AST, ALT, total bilirubin, direct and indirect bilirubin, total protein, albumin, CPK, bicarbonate, blood urea nitrogen (BUN), chloride, creatinine, glucose, potassium, sodium, amylase (reflex lipase testing is performed in subjects with total amylase > 1.5 × ULN)
    - Calcium, phosphorus, magnesium (Screening and Day 1)

- Metabolic assessments: Fasting (no food or drinks, except water, at least 8 hours prior to blood collection) glucose and lipid panel (total cholesterol, HDL, direct LDL, and triglycerides) collected at Day 1, Weeks 12, 24, and 48, and every 24 weeks thereafter, End of Blinded Treatment Visit, and every 24 weeks in the OL extension phase
  - If the subject has not fasted prior to the visit, the visit may proceed, but the subject must return within 72 hours in a fasted state to draw blood for the metabolic assessments
- eGFR according to the Cockcroft-Gault formula:

Male: 
$$\frac{(140 - \text{age in years}) \times (\text{wt in kg})}{72 \times (\text{serum creatinine in mg/dL})} = \text{creatinine clearance (CLcr) (mL/min)}$$

$$\frac{(140 - \text{age in years}) \times (\text{wt in kg})}{72 \times (\text{serum creatinine in umol/L}) \times 0.6786} = \text{CLcr (mL/sec)}$$
Female: 
$$\frac{(140 - \text{age in years}) \times (\text{wt in kg})}{72 \times (\text{serum creatinine in mg/dL})} \times 0.85 = \text{CLcr (mL/min)}$$

$$\frac{(140 - \text{age in years}) \times (\text{wt in kg})}{72 \times (\text{serum creatinine in umol/L}) \times 0.6786}$$

- Hematology profile: complete blood count (CBC) with differential and platelet count
- CD4+ cell count and percentage
- Plasma HIV-1 RNA
- HBV blood panel (Screening, Week 48, every 48 weeks through End of Blinded Treatment Visit, and Weeks 48OL, 96OL): Hepatitis B virus surface antigen (HBsAg), Hepatitis B virus surface antibody (HBsAb) and Hepatitis B virus core antibody (HBsAb)

The following tests will be conducted by the central laboratory if the following criteria are met:

- If positive HBsAg: reflex testing for plasma HBV DNA, Hepatitis B virus e-antigen (HBeAg) (if negative, reflex Hepatitis B virus e-Antibody [HBeAb]), and quantitative HBsAg

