#### **8.6.3.** Laboratory Evaluations

Selected laboratory data (using conventional units) will be summarized using only observed data. Absolute values and changes from baseline at all scheduled visits will be summarized.

Graded laboratory abnormalities will be defined using the grading scheme defined in Grading of laboratory abnormalities attached in Appendix 4.

Incidence of treatment-emergent laboratory abnormalities, defined as values that increase at least 1 toxicity grade from baseline at any time post baseline up to, and including, the date of last dose of study drug plus 30 days, will be summarized by treatment. If baseline data are missing, then any graded abnormality (ie, at least a Grade 1) will be considered treatment emergent. The maximum postbaseline toxicity grade will be summarized by laboratory parameter.

Laboratory abnormalities that occur before the first dose of study drug or after the last dose of study drug plus 30 days will be included in a data listing.

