- o. Chemistry profile: alkaline phosphatase, AST, ALT, total bilirubin, direct and indirect bilirubin, total protein, albumin, CPK, bicarbonate, BUN, calcium, chloride, creatinine, glucose, phosphorus, magnesium, potassium, sodium, and amylase (reflex lipase testing is performed in subjects with total amylase > 1.5 × ULN). After Day 1, calcium, phosphorous, and magnesium will not be collected. Analyses of glucose will be done as part of the fasting metabolic assessments, and not as part of the chemistry profile at Day 1, Weeks 12, 24, 48, post Week 48 (every 24 weeks), and End of Blinded Treatment, Week 24OL, Week 48OL, Week 96OL.
- p. CBC with differential and platelet count.
- q. Fasting (no food or drinks, except water, at least 8 hours prior to blood collection) glucose and lipid panel (total cholesterol, HDL, direct LDL, triglycerides). If the subject has not fasted prior to the visit, the visit may proceed, but the subject must return within 72 hours in a fasted state to draw blood for the metabolic assessments.
- r. Metabolic assessments during the post Week 48 will be done every 24 weeks.
- s. Hepatitis C virus serology. Subjects who are HCVAb positive will have a HCV RNA test performed.
- t. HBV blood panel will be performed at Screening, Week 48, every 48 weeks through End of Blinded Treatment Visit, and Weeks 48OL, 96OL: HBsAg, HBsAb, HBcAb

CONFIDENTIAL Page 90 28 June 2018

- u. **For subjects who are HBV co-infected at any visit:** The following HBV Blood panel will be conducted by the central laboratory: HBsAb, HBsAg (qualitative and quantitative), and HBeAg (if negative, reflex HBeAb)
  - For subjects who are NOT HBV co-infected at any visit: The following HBV Blood panel will be conducted by the central laboratory: HBsAb, HBcAb, and HBsAg. Subjects who are HBsAg or HBcAb positive will have a reflex test for HBV DNA (viral load)
- v. For subjects who are HBV co-infected at any visit: Plasma HBV DNA at every visit (including OL extension period [not collected at Screening and 30-day Follow-up])
- w. Randomization may be performed up to 3 days prior to the in-clinic Day 1 visit provided that all screening procedures have been completed and subject eligibility has been confirmed.
- x. Initiation of the first dose of study drug is to take place in-clinic following completion of study procedures at the Day 1 visit.
- y. Open label study drug, B/F/TAF FDC will be dispensed to subjects participating in the OL extension for up to 96 weeks.

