# Study Day 1 for the all B/F/TAF analysis is defined as

- For subjects who actually received B/F/TAF in the randomized phase of this study (ie, B/F/TAF group), **Study Day 1** for the all B/F/TAF analysis is defined as the day when the first dose of B/F/TAF in the randomized phase was taken, as recorded on the Study Drug Administration eCRF form.
- For subjects who actually received DTG + F/TAF in the randomized phase of this study and then receive at least 1 dose of B/F/TAF in the extension phase (ie, DTG + F/TAF to B/F/TAF group), **Study Day 1** for the all B/F/TAF analysis is defined as the day when the first dose of B/F/TAF in the extension phase was taken (ie, OL B/F/TAF), as recorded on the Study Drug Administration eCRF form.

Last Dose Date for the All B/F/TAF Analysis is the latest of B/F/TAF (including both randomized phase and open label phase) end dates recorded on the Study Drug Administration eCRF form.

If the last dose date for the all B/F/TAF analysis is missing (eg, only year of last dose date is known or completely missing due to lost to follow-up), the latest of the B/F/TAF (including both randomized phase and open label phase) start dates and end dates, the latest clinical and laboratory visit dates, excluding the 30-day follow-up visit date, will be used to impute the last dose date.

**Study Days** are calculated relative to Study Day 1 for the randomized phase analysis. For events that occurred on or after the Study Day 1 date, study days are calculated as (visit date minus Study Day 1 plus 1). For events that occurred prior to Study Day 1 for either analysis, study days are calculated as (visit date minus Study Day 1).

**Last Study Date** is the latest of the study drug (including DTG + F/TAF, and B/F/TAF in both randomized phase and open label phase) start dates and end dates, the clinic visit dates, and the laboratory visit dates, including the 30-day follow-up visit date.

**Baseline Value** is defined as the last nonmissing value obtained on or prior to Study Day 1 for the randomized phase analysis or the all B/F/TAF analysis, as appropriate. Subjects who actually received DTG + F/TAF in the randomized phase and received at least 1 dose of B/F/TAF in extension phase will have a baseline for Randomized Phase Analysis and a new baseline value for the all B/F/TAF analysis.

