#### 13) Toxicity Grades:

- a) For toxicity grade summaries, include all post-baseline graded results up to 30 days after the last dose of study drug, not just those used in by-visit summaries.
- b) For glucose grading, as specified in SAP Section 7.2.2.1, the treatment-emergent flag cannot be determined for nonfasting glucose (including glucose results without a known fasting status). As a result, these records will be excluded from the "Maximum Treatment-emergent Toxicity Grade" summary in the "Treatment-emergent Laboratory Abnormalities" or "Treatment-emergent Grade 3 or 4 Laboratory Abnormalities" summary tables. In addition, fasting glucose and non-fasting glucose will be listed as two separate laboratory tests in the "Laboratory Abnormalities" and "Grade 3 or 4 Laboratory Abnormalities" listings. Only a maximum postbaseline toxicity flag will be displayed and the treatment-emergent flag will not be displayed for nonfasting glucose as the treatment-emergent flag cannot be determined for nonfasting glucose.

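### The SAP says treatment emergence cannot be determined for nonfasting glucose, although its own baseline rule accepts the Screening value; the row it reports instead includes stable pre-existing hyperglycaemia

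*SAP*

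**What the plan says.** SAP 7.2.2.1 sets the rule for this test: "Maximum postbaseline grade, instead of treatment-emergent grade, for nonfasting glucose (including glucose results without a known fasting status) will be summarized". The reason given is that "nonfasting glucose was not assessed at baseline visit for most of the subjects", from which the SAP concludes that nobody can say whether an abnormality is treatment-emergent in these subjects. SAP Appendix 8, item 13b, repeats the conclusion for the tables and listings: "the treatment-emergent flag cannot be determined for nonfasting glucose (including glucose results without a known fasting status"). The same item keeps these records out of the treatment-emergent grade summary, withholds the flag, and treats fasting and nonfasting glucose as two separate tests.

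For laboratory tests in general, protocol 8.6.3 asks for the incidence of treatment-emergent abnormalities, "defined as values that increase at least 1 toxicity grade from baseline at any time post baseline". SAP 3.8.1 says that a baseline value "is defined as the last nonmissing value obtained on or prior to Study Day 1", and SAP 7.2.1 gives the same rule for laboratory tests. SAP 7.8 reports no departure from the protocol's safety analyses.

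**The concern.** The SAP's reason refers to the baseline visit, but its definition of baseline is not tied to that visit. If a nonfasting glucose exists at any time up to first dose, the definition accepts it and the usual comparison of grades can be made.

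What is at stake is how one safety row reads. A maximum postbaseline grade takes no account of the grade before dosing. A subject who enters with raised glucose and does not change is counted alongside a subject whose glucose rises on study drug. The row would stand near rows built on a different rule, and the protocol's treatment-emergent incidence would be missing for this test without being recorded as a change.

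**Working it through.** The documents give no figure to reproduce on this point, so the check traces the schedule against the definitions and then grades example subjects.

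**Is there a nonfasting glucose before dosing?**

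- The protocol synopsis (Study Procedures/Frequency) places chemistry at Screening: "Laboratory analyses (hematology, chemistry, and urinalysis), HIV-1 RNA, CD4+ cell count and percentage, and complete or symptom-directed physical examinations will be performed at the Screening". The Appendix 2 table agrees.
- Protocol 6.10.1 lists glucose in the chemistry profile: "chloride, creatinine, glucose, potassium, sodium, amylase".
- Protocol Appendix 2, footnote o, moves glucose elsewhere at certain visits: "Analyses of glucose will be done as part of the fasting metabolic assessments, and not as part of the chemistry profile at Day 1", then Weeks 12, 24, 48 and later fasting visits. Screening is not on that list.
- Protocol 6.10.1 starts fasting collection at Day 1, so the Screening draw carries no fasting requirement.
- Inclusion criteria 7, 10, 11 and 13 need creatinine, transaminases, bilirubin and amylase, so the Screening panel should exist for essentially every randomized subject.

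Through Week 48 the postbaseline chemistry visits are Weeks 4, 8, 12, 24, 36 and 48. Removing the fasting visits (12, 24, 48) leaves Weeks 4, 8 and 36 for scheduled nonfasting glucose.

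**Does the SAP's baseline rule accept the Screening value?**

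- The rule in SAP 3.8.1 and 7.2.1 has no earliest date, and SAP Table 2 gives the chemistry baseline window only an upper limit, Day 1. Screening falls within 30 days before Day 1 (protocol 6.2.1).
- Because fasting and nonfasting glucose are separate tests, the Day 1 fasting result does not displace the Screening result as baseline for the nonfasting test.
- Results of unknown fasting status are pooled with nonfasting, so a Screening result without recorded status also qualifies.
- The SAP already relies on Screening this way. HBV and HCV serology are drawn before dosing only at Screening, yet they define baseline coinfection in SAP 8.1 and 8.2.

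**What difference does it make?** The nonfasting hyperglycaemia scale in protocol Appendix 4 is Grade 1 from 116 to 160 mg/dL, Grade 2 above 160 to 250, Grade 3 above 250 to 500, and Grade 4 above 500. The planned row counts a subject if the maximum postbaseline grade is at least 1. The standard rule counts a subject if the maximum postbaseline grade is at least the baseline grade plus 1. The glucose values below are illustrations, not trial data.

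| Screening (mg/dL) | Weeks 4, 8, 36 (mg/dL) | Baseline grade | Maximum grade | Planned row | Standard rule |
|---|---|---|---|---|---|
| 180 | 180, 180, 180 | 2 | 2 | counted | not counted |
| 130 | 130, 125, 140 | 1 | 1 | counted | not counted |
| 100 | 130, 100, 100 | 0 | 1 | counted | counted |
| 180 | 270, 180, 180 | 2 | 3 | counted | counted |
| 100 | 100, 100, 100 | 0 | 0 | not counted | not counted |

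The direction needs no assumption. Any subject who meets the standard rule has a maximum grade of at least 1, so the planned count can only equal or exceed the treatment-emergent count.

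The size does need one, because the documents give no distribution of Screening glucose. If a proportion p of the 565 treated subjects (SAP Appendix 3) had an unchanged pre-existing grade of 1 or more, the excess would be 565 × p: 11.3 at 2%, 28.3 at 5%, 56.5 at 10% and 113 at 20%. These values of p are assumptions that show scale only.

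**The case against.** Much of the case for leaving the plan alone is sound, and it rules out several stronger readings.

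- A reader might infer that pre-existing hyperglycaemia is reported as treatment-emergent. Item 13b prevents that by excluding these records from the treatment-emergent grade summary and showing no flag. The SAP's default for a missing baseline would have called every Grade 1 or higher value treatment-emergent, and the SAP avoids that too. What remains is a labelling risk: Appendix 8, item 17, lists nonfasting glucose among the labels for the treatment-emergent tables.
- A reader might infer that the stated reason is false. It is literally true of the Day 1 visit; only the inference drawn from it fails.
- A reader might infer that a maximum-grade summary is itself a protocol departure. Protocol 8.6.3 also plans maximum postbaseline grade by laboratory parameter. The gap is only the missing treatment-emergent incidence for this test.
- A reader might infer that a glucose signal would be lost. Fasting glucose has a Day 1 baseline, a treatment-emergent grade summary, and between-arm Wilcoxon tests of change (SAP 7.2.3). The nonfasting row is descriptive and uses one rule in both randomized arms.
- A reader might want a percentage for the miscounting. Any such figure would rest on assumed diabetes prevalence and glucose variability. It would also depend on the laboratory's normal range, since values within it are Grade 0 and the documents do not give that range.

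Two practical objections also stand. One casual glucose is a noisy baseline, so some apparent grade increases will be ordinary within-subject variation. And Screening does not serve the group switching from DTG+F/TAF to B/F/TAF, whose baseline for the all B/F/TAF analysis is reset at the first open-label dose.

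**Conclusion.** The statement that treatment emergence cannot be determined is wrong for every subject who has a nonfasting or unknown-status glucose on or before first dose. The SAP's own definitions supply both the baseline and the rule. As planned, the row mixes stable pre-existing hyperglycaemia with new abnormalities and leaves out an incidence the protocol specifies, while SAP 7.8 records no change.

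This rests on the Screening panel having been drawn as scheduled. Subjects recorded as fasting at Screening have no nonfasting baseline from that draw, and the documents do not say how many there are. The number of subjects miscounted cannot be computed from the documents. Severity is low, and no efficacy conclusion depends on this row.

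**What to change.** Amend SAP 7.2.2.1 and Appendix 8, items 13b and 17, as follows.

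1. For each analysis, define the nonfasting baseline as the last nonfasting or unknown-status glucose on or before that analysis's first dose date. For the randomized phase this is normally Screening. For the DTG+F/TAF to B/F/TAF group it is the last such on-study value before the first open-label dose.
2. For subjects with such a value, report treatment-emergent grade by the standard rule of an increase of at least 1 grade.
3. Keep maximum postbaseline grade as a separately labelled row, footnoted that it includes pre-existing abnormalities. Use it alone for subjects with no such baseline.
4. Correct the stated rationale. If any subjects remain without treatment-emergent reporting, record that in SAP 7.8.

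The cost is SAP wording and one re-derived flag from data already collected. The downside is a baseline made of one casual glucose value, up to 30 days old at Day 1. For the switch group it may be older. After Week 48, visits are every 12 weeks with fasting glucose every 24, so scheduled nonfasting draws fall at Weeks 36, 60, 84 and so on, which are 24 weeks apart. The End of Blinded Treatment Visit is itself a fasting visit. A footnote giving the age of the baseline value would be enough.
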